6.5 Safety Analysis

Adverse events will be reported for the short-term (Treatment Period) and for the long-term (Post-Treatment Period). The Treatment Period will be defined at the Day of 1st procedure bronchoscopy till 6 weeks after the last procedure bronchoscopy. The Post-Treatment Period will begin at the end of the Treatment Period i.e. at beginning at 6 weeks after the last procedure bronchoscopy. Annual visits will be based on a 52 week period beginning at 6 weeks after the last procedure bronchoscopy.

An adverse event is defined as any sign, symptom, illness, clinically significant abnormal laboratory value, or other adverse medical event that appears or worsens in a subject during a clinical study, regardless of whether or not it is considered related to the procedure used as part of the protocol.

All adverse events reported during the study will be listed, documenting course, severity, possible relationship to procedure, and outcome. Verbatim terms will be classified to preferred terms and system organ classes using the MedDRA dictionary. The preferred terms and system organ classes will then be tabulated by the treatment period and each year of follow-up. All reported adverse events will be summarized by the number of subjects reporting adverse events, system organ class, preferred term, severity, duration, and relationship to procedure.

In addition to the complete tabulation of adverse events for all subjects enrolled in the study, adverse events will also be tabulated separately for the subsets of subjects enrolled in sites in the United States and the sites in Canada.

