3. **Excess Mucus:** There is a potential for excess mucus production in response to treatment. In general, it is expected that coughing will clear any excess mucus. It is possible that the mucus may, however, become inspissated (thickened) and get stuck in the airway. Inspissated mucus may cause atelectasis and increased chances for pneumonia or infection. In the event that any of these were to occur, there may be a need for intubation, therapeutic bronchoscopy, or treatment with antibiotics.

All subjects will be instructed to contact their Investigator or a member of the Clinical Study Staff with any breathing or other medical problems that occur during the follow-up period. In the event inspissated mucus is suspected, the subject will be treated as indicated with chest physical therapy at first. Symptomatic subjects with persistent atelectasis will be considered for therapeutic bronchoscopy.

4. **Pneumonia or infection:** There is a risk of developing pneumonia as a result of excess mucus production (as described above) or other theoretical reasons, such as impairment of the ability for the lung to clear mucus.

During preclinical evaluations of the Alair System, a single case of bronchopneumonia occurred in a dog more than two years after the last treatment. This event was thought to be unrelated to treatment with the Alair System.

5. **Impaired gas exchange:** It is possible that treatment with the Alair System can result in a decrease in the ability of the lungs to exchange gases.

Based on previous published studies involving bronchoscopy in asthmatic patients, it is believed that patients may experience a transient drop in the amount of oxygen in the blood post treatment (*Spanevello et al.*, 1998; *Van Vyve et al.*, 1992). In previous studies with the Alair System, occasional transient decreases in SpO₂ have been noted immediately post treatment, which resolved either spontaneously or with administration of supplemental oxygen during the protocol-specified post-procedure monitoring period.

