4.6 Safety Analyses

Adverse events will be reported for the short-term (treatment period) and for the long-term (post-treatment period). The treatment period will be defined as the day of 1st procedure bronchoscopy till 6 weeks (41 days) after the last procedure bronchoscopy. The post-treatment period will begin at the end of the treatment period (i.e. beginning at 6 weeks [42 days] after the last procedure bronchoscopy) for patients who have at least one post-treatment visit (i.e. 6-week visit or later). Patients who do not have a post-treatment visit will not be counted in post-treatment summaries. Annual summaries will be based on a 365-day period beginning at 6 weeks (42 days) after the last procedure bronchoscopy.

Verbatim terms will be classified to preferred terms and system organ classes using the MedDRA dictionary. The preferred terms and system organ classes will then be tabulated by the treatment period and each year of follow-up. All reported adverse events will be summarized by the number of subjects reporting adverse events, system organ class (SOC), preferred term, severity, seriousness, duration, and relationship to procedure. In the summary of MedDRA coded terms, for the preferred terms listed in Table 3, the system organ class will be changed to “Respiratory, thoracic and mediastinal disorders”. The reason for the change in SOC is to conservatively report respiratory-related adverse events since the preferred terms in Table 3 represent events that could be related to respiratory function.

Table 3. Preferred Term that will have the system organ class (SOC) changed to “Respiratory, thoracic and mediastinal disorders” for summary tables

System Organ Class Code	System Organ Class	Preferred Term Code	Preferred Term
10005329	Blood and lymphatic system disorders	10020094	Hilar lymphadenopathy
10007541	Cardiac disorders	10007617	Cardio-respiratory arrest
10018065	General disorders and administration site conditions	10008469	Chest discomfort
		10008479	Chest pain
		10062501	Non-cardiac chest pain
10021881	Infections and infestations	10001076	Acute sinusitis
		10006451	Bronchitis
		10053160	Bronchitis viral
		10009137	Chronic sinusitis
		10022000	Influenza
		10023874	Laryngitis
		10067321	Laryngitis fungal
		10024968	Lower respiratory tract infection
		10025028	Lung abscess
		10028810	Nasopharyngitis

System Organ Class Code	System Organ Class	Preferred Term Code	Preferred Term
		10034835	Pharyngitis
		10034839	Pharyngitis streptococcal

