		10035664	Pneumonia
		10035728	Pneumonia pneumococcal
		10035730	Pneumonia primary atypical
		10062352	Respiratory tract infection
		10060693	Respiratory tract infection bacterial
		10039083	Rhinitis
		10040753	Sinusitis
		10060841	Sinusitis bacterial
		10044008	Tonsillitis
		10046306	Upper respiratory tract infection
		10047473	Viral pharyngitis
		10051513	Viral sinusitis
		10047482	Viral upper respiratory tract infection
10022117	Injury, poisoning and procedural complications	10009913	Collapse of lung
		10069363	Traumatic lung injury
10028395	Musculoskeletal and connective tissue disorders	10050819	Musculoskeletal chest pain
10029104	Neoplasms benign, malignant and unspecified (incl cysts and polyps)	10062042	Lung neoplasm
10029205	Nervous system disorders	10034018	Parosmia
		10040744	Sinus headache

In addition to the complete tabulation of adverse events for all subjects enrolled in the study, adverse events will also be tabulated separately for the subsets of subjects enrolled in sites in the United States and the sites in Canada.

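### SAP 4.6 overwrites the MedDRA class of 36 preferred terms in the summary tables instead of adding a respiratory grouping, so the Infections row is understated and no planned row counts subjects with any infection

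*SAP*

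**What the plan says.** Protocol 6.5 sets the tabulation rule. "Verbatim terms will be classified to preferred terms and system organ classes using the MedDRA dictionary", and then "The preferred terms and system organ classes will then be tabulated by the treatment period and each year of follow-up". It mentions no reassignment of classes.

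SAP 4.6 repeats the coding sentence and adds an exception: "for the preferred terms listed in Table 3, the system organ class will be changed to" the respiratory, thoracic and mediastinal class. The Table 3 caption ("Preferred Term that will have the system organ class (SOC) changed to" that class) limits the change to summary tables. The stated motive is caution: "The reason for the change in SOC is to conservatively report respiratory-related adverse events". The revision history records that Table 3 came in with SAP version AB.

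Preferred-term rows are kept. SAP 4.6 says "All reported adverse events will be summarized by the number of subjects reporting adverse events, system organ class (SOC), preferred term, severity, seriousness", followed by duration and relationship to procedure.

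Protocol 9.1 lists pneumonia or infection as a separate risk item: "There is a risk of developing pneumonia as a result of excess mucus production (as described above) or other theoretical reasons".

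Protocol 5.6 and SAP 2.2 define the respiratory adverse event endpoint by association with the respiratory system. Neither cites a class or a term list.

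**The concern.** Moving a term is not the same as adding it to a second grouping. Each moved term raises the Respiratory row or leaves it unchanged, and lowers its own class row or leaves it unchanged. The choice is therefore conservative for one row and the opposite for eight others, and one of those eight is the class that carries a named risk of the procedure.

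A reader of the final tables would see a row labelled Infections that lacks the lung and airway infections on the list. That reader would have no direct way to learn how many subjects had an infection in the treatment period or in a given year. The study does collect detail on this. Protocol 8.2 asks sites whether an infection was in the upper or lower respiratory tract, and protocol 8.3 sets diagnostic criteria for pneumonia. The planned summaries do not bring that detail together by subject.

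**Working it through.** The plan states no figure for this point, so there is nothing to reproduce. The check is a count of Table 3 and a test of what can be recovered from the rows that remain.

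**1. Count of Table 3, by original class**

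| Original class | Terms moved |
|---|---|
| Infections and infestations | 25 |
| General disorders and administration site conditions | 3 |
| Injury, poisoning and procedural complications | 2 |
| Nervous system disorders | 2 |
| Blood and lymphatic system disorders | 1 |
| Cardiac disorders | 1 |
| Musculoskeletal and connective tissue disorders | 1 |
| Neoplasms | 1 |
| **Total** | **36** |

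The infection share is 25/36 = 69%. It runs from minor illness ("Viral upper respiratory tract infection", nasopharyngitis) to pneumonia and lung abscess. The other 36 − 25 = 11 terms are not from the Infections class.

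**2. Which planned row gives subjects with an infection?**

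- The Infections row holds only the infections that are not in Table 3.
- The Respiratory row mixes the 25 infection terms with non-infectious events.
- Each preferred-term row is correct for its own term only.

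No row therefore gives subjects with any infection or with any respiratory infection.

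**3. Can the number be rebuilt from the preferred-term rows?**

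One subject can have several terms, so the rows only bound the number of subjects with at least one:

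largest term count ≤ subjects with at least one ≤ smaller of N and the sum of the term counts.

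To show the width, take the lower limits of the frequency bands that protocol 9.1 gives for the pivotal trial, within 6 weeks of the procedure. These are upper and lower respiratory tract infection at 5% each, sinusitis, bronchitis and influenza at 3% each, and pneumonia at 1%. Applying these limits to this study, with the other 19 infection terms set to zero, is an assumption made for illustration.

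- Lower bound: 5%.
- Upper bound: 5 + 5 + 3 + 3 + 3 + 1 = 20%.
- With N = 250: 12.5 to 50 subjects. With N = 300: 15 to 60 subjects.

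If the six terms were independent, the value would be 1 − 0.95² × 0.97³ × 0.99 = 18.5%. Nothing in the documents supports independence, so the rows alone leave a fourfold range. Subjects with any infection would be less certain still, because the remaining Infections row overlaps with these terms to an unknown extent.

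**4. Protocol against SAP**

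Protocol 6.5 tabulates by MedDRA class. SAP 4.6 tabulates 36 terms under a class other than the one shown for them in Table 3, and plans no parallel table. The Infections, Cardiac and Neoplasms rows, among others, would therefore differ from what the protocol describes.

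**The case against.** The strongest reply is that this is only presentation. The change is limited to summary tables, Table 3 prints each term's original class and code, the reason is given, and the change is logged. Pneumonia, lower respiratory tract infection and lung abscess keep their own rows with subject counts. Protocol 6.5 also lists every adverse event, respiratory serious events get narratives, and protocol 8.1 has the safety board review all respiratory events. All of this stands. A reader might infer that infection is left with no valid subject count at all. The documents do not support that: only the aggregate is missing, and it can be derived from the coded data.

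A second reply is that the unaltered Infections class would mix respiratory infections with infections elsewhere, so standard coding alone would not give a respiratory-infection count either. That is correct, and it is why the fix needs a subtotal as well as the restored classes. It does not justify a class row that omits 25 of its own terms.

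A reader might also infer that colds and sinusitis dilute the respiratory adverse event endpoint and hide a late rise in airway events. The documents do not support this, for four reasons:

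- The endpoint definition covers any illness associated with the respiratory system, and the pivotal-trial summary in protocol 3.1 already counts upper and lower respiratory tract infection as respiratory events.
- Neither document ties the endpoint to the reassigned class.
- Any size for the effect would need infection shares that the documents do not give, and it would not apply to event rates, where extra events add in full.
- Airway worsening is also followed through exacerbations, emergency visits, hospitalizations and FEV₁.

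Including infections in a respiratory total is reasonable. Removing them from their own class is the problem.

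**Conclusion.** The point holds as a minor safety-reporting improvement. In the summary tables, 36 terms lose their MedDRA class and 25 of them leave Infections. The eight source rows can only be understated, and no planned row gives subjects with any infection or any respiratory infection per period. This departs from the tabulation in protocol 6.5 and touches a risk that protocol 9.1 names.

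The term count comes directly from Table 3 and needs no assumption. The 5% to 20% range illustrates what preferred-term rows alone can tell; it rests on pivotal-trial frequency bands and is not a forecast for this study. The conclusion also assumes that no table under the original classes is intended, since neither document mentions one alongside Table 3. The secondary endpoints carry no formal hypothesis, and the primary endpoint, sample size and power are unaffected.

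**What to change.** Amend SAP 4.6 as follows:

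1. Keep the class and preferred-term tables as MedDRA codes them. This restores the Infections, Cardiac, Neoplasms and other source rows, and makes subjects with any infection directly readable.
2. Present a separate respiratory-related summary, by treatment period and by year, made up of the MedDRA Respiratory class plus the Table 3 terms. Give subject-level subtotals for respiratory infections (the 25 Table 3 infection terms) and for non-infectious respiratory events (the Respiratory class plus the other 11 terms). A subject with both counts once in each subtotal and once in the total.
3. State that this grouping defines the respiratory adverse event rates and proportions in SAP 2.2.

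This keeps the sponsor's cautious respiratory total. It needs no new data or recoding, and SAP 4.7 already provides the route: an amended plan approved before the analyses are performed. The cost is SAP wording and one extra summary table.

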4.7 Changes to Planned Analyses

Any changes to the planned statistical analyses made prior to performing the analyses will be documented in an amended statistical analysis plan approved before performing the analyses. Changes from the planned statistical methods after performing the analyses will be documented in the clinical study report along with a reason for the deviation.

5 VALIDATION

All clinical data reports generated per this plan will be validated per 90702587, Global WI: Clinical Data Reporting Validation.

6 PROGRAMMING CONSIDERATIONS

6.1 Statistical Software

Statistical data review will be performed by the sponsor. Statistical analyses will be performed using SAS System software, version 9.2 or later (Copyright © 2000 SAS Institute Inc., SAS Campus Drive, Cary, North Carolina 27513, USA. All rights reserved).

6.2 Format of Output

Results of analysis will be output programmatically to Word documents from SAS with no manual intervention. All output for the final statistical report will be in the form of a Word document containing tables, figures, graphs, and listings, as appropriate.

6.3 Methods for Handling Missing Data

All patients who are enrolled will be eligible for evaluation, regardless of the treatment that ensues. The effect of missing data for the primary endpoint will be evaluated with a sensitivity (tipping-point) analysis (Section 2.1.3). Statistical models that account for censored data will be employed in appropriate circumstances (e.g., for time-to-event outcomes). Outlier values will be evaluated for their validity; all data will be included unless judged to be invalid.

When calculating rates of adverse events, missing and partial dates will be handled as shown below:

Partial Date Description	Action Taken
Entire onset date is missing	The procedure date will be used for the onset date.
The month and the day of the month are missing but the year is available	January 1 will be used for the month and day of the onset date. However, if the imputed date falls before the procedure date, then the procedure date will be used for the onset date.
Day is missing, but the month and year are available	The 1 st will be used as the day of the onset date. However, if the imputed date falls before the procedure date, then the procedure date will be used for the onset date.

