Eligible subjects who are enrolled in the study will undergo bronchial thermoplasty over three treatment sessions to allow for a careful and sequential treatment of the entire lung. For each treatment session, subjects will take 50mg of oral prednisone or equivalent, for five days to include the three days before, the day of, and the day after the treatment session (prophylactic indication).

The bronchoscopy procedure will be administered as per the *Alair System Instructions for Use* with local anesthesia and moderate sedation as detailed in Section 7.3.7 below. The treatment sessions will be separated by a follow-up visit at 2 weeks after each bronchoscopy session. During the first session, the right lower lobe (RLL) of the lung will be treated. The right middle lobe will not be treated. During the second treatment session, the left lower lobe (LLL) of the lung will be treated. During the third treatment session, both the right upper lobe (RUL) and the left upper lobe (LUL) including the lingula will be treated.

At the time of the second and third treatment sessions, airways that were treated during the previous treatment session will be carefully examined and any findings will be documented. If any clinically significant findings are observed, the treatment session will be postponed until complete resolution of these findings (see Section 7.3.6). Complete resolution of any

findings must be confirmed and documented in a subject's medical records before subsequent Alair treatments commence.

Bronchial thermoplasty is an "out-patient procedure". Clinical study sites should generally schedule treatments in the morning to allow for post-procedure monitoring of subjects for a minimum of four hours before being released to home. Subjects may be monitored for longer than four hours and, if clinically indicated hospitalized overnight; however, overnight hospitalizations simply for observational reasons will not be considered as an adverse event.

Following each treatment session, subjects will be contacted by telephone on post-treatment Day 1, Day 2, and Day 7. Subjects will be instructed to contact the Investigator or a member of the clinical site staff at each site to report any unusual symptoms at any time following a treatment session.

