7.3.4 Prior to Performing Bronchial Thermoplasty with the Alair System

- Ensure that subject has not had an asthma exacerbation that was treated with systemic corticosteroids within the last two weeks.

Do not schedule the treatment session if the subject had an asthma exacerbation requiring systemic corticosteroids within the last 2 weeks and their post-bronchodilator FEV₁ is not back to within 10% of baseline/enrollment levels.

- Ensure that subject has not had a lower respiratory tract infection within the last six weeks.

Do not schedule the treatment session if the subject had a lower respiratory tract infection that resolved within the last 6 weeks.

- Ensure that subject has not had an upper respiratory tract infection within the last one (1) week.

Do not schedule the treatment session sooner than one (1) week after resolution of symptoms from a recent upper respiratory tract infection.

- Prescribe 5 doses of 50mg each of oral prednisone or equivalent to be taken on the three days prior to treatment, day of treatment, and day after treatment (prophylactic indication).

Document in subject's study notes and treatment-related CRF/eCRFs; do not add as an additional concomitant medication.

- Schedule the treatment session to allow for required minimum of 4 hours monitoring of subject prior to discharge.
- Subject must continue taking their maintenance asthma medications of inhaled corticosteroids and LABA as prescribed.
- If antibiotics are prescribed for prophylaxis according to institutional policies at the time of the treatment, the antibiotic usage should be noted on the Medication Log for this subject, but this use of antibiotics will NOT trigger the actions called for in Section 8.0 Adverse Events, with regard to infections.

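### SAP 6.3 moves partly dated adverse events into the Treatment Period even when the recorded month or year shows that they began before the first procedure

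*SAP*

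**What the plan says.** SAP 6.3 introduces its date table with "When calculating rates of adverse events, missing and partial dates will be handled as shown below". For a known month and year it imputes the first of the month. For a known year only, "January 1 will be used for the month and day of the onset date". Both rows end with the same floor: "However, if the imputed date falls before the procedure date, then the procedure date will be used for the onset date". A wholly missing onset is also set to the procedure date. Nowhere does the section say which of the three procedures is meant.

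SAP 4.6 sets the window that the imputed dates feed: "The treatment period will be defined as the day of 1st procedure bronchoscopy till 6 weeks (41 days) after the last procedure bronchoscopy". It then states: "The preferred terms and system organ classes will then be tabulated by the treatment period and each year of follow-up". There is no pre-procedure column.

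SAP 6.4 step 3 sends partial severe exacerbation dates back to 6.3. Step 4 merges exacerbations according to the gap between one resolution and the next onset, and step 5 assigns each to a period by its onset date.

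Events before the first procedure can be in the data. Protocol Table 2 ticks AE solicitation at Screening/Enrollment. Protocol 8.0 collects AEs throughout the study and does not tie their definition to the procedure.

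**The concern.** A floor at the procedure date is reasonable when the known month or year contains that date, because the event may then have started on either side of it. The rule as written goes further and overrides information that is not missing. If the recorded month is wholly before the first procedure, the event is known to be pre-treatment, yet it becomes an event on the day of treatment.

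Whether a pre-treatment event counts as a Treatment Period AE then depends on how completely its date was written down, not on when it happened. Short-term safety is a stated objective of the study (Protocol 4.0), and the Treatment Period tables are where it is reported.

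The protocol itself expects events between enrollment and session 1. Section 7.3.3 requires a wait of at least 4 weeks after oral steroids for an exacerbation during the enrollment evaluations. Section 7.3.4 bars scheduling if a lower respiratory tract infection resolved within the last 6 weeks. With such gaps, an onset in an earlier calendar month than session 1 is realistic.

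**Working it through.** The plan gives no figure to reproduce, so the check applies the rules to dates.

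**Assumed dates.** Session 1 is on 20 May 2012. Sessions are 21 days apart, the minimum in Protocol 7.3.5, so session 2 is on 10 June and session 3 on 1 July. By SAP 4.6 the Treatment Period runs from 20 May to 1 July + 41 days = 11 August 2012.

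**Rule.** Imputed onset = first possible day of the known month or year. If that is before the procedure date, onset = procedure date.

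With the procedure date read as session 1:

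| Recorded onset | First possible day | After the floor | Known to predate session 1? | Counted in Treatment Period? |
|---|---|---|---|---|
| 2011 | 1 Jan 2011 | 20 May 2012 | Yes | Yes |
| Dec 2011 | 1 Dec 2011 | 20 May 2012 | Yes | Yes |
| Apr 2012 | 1 Apr 2012 | 20 May 2012 | Yes | Yes |
| 15 Apr 2012 (full date) | not imputed | not applied | Yes | No |
| May 2012 | 1 May 2012 | 20 May 2012 | No | Yes |
| 2012 | 1 Jan 2012 | 20 May 2012 | No | Yes |

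The first three rows are the error, and the fourth shows the inconsistency. In the last two rows the floor does its proper job.

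**Which procedure.** If the procedure date is read as session 2 or 3, the first three rows move to 10 June or 1 July. Both dates are inside the Treatment Period, so the misclassification does not depend on the reading. The ambiguity does matter for events between sessions. An AE recorded as June 2012 is imputed to 1 June. It stays there if session 1 is meant but moves to 1 July if session 3 is meant.

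**Severe exacerbations (SAP 6.4).** Suppose the April 2012 AE matches a course of oral corticosteroid and has a recorded resolution of 25 April 2012. The reset onset is 20 May. Length = 25 April − 20 May = −25 days. The gap test in step 4 and the period assignment in step 5 would both use that onset.

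**Effect on the primary endpoint.** Under any of the three readings the reset onset falls between day 0 of session 1 and day 0 of session 3. Year 1 starts 42 days after the last procedure. A pre-treatment event moved by the floor therefore cannot enter Years 1 to 5.

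**Size.** The documents give no count of such AEs. Planned enrollment is 250 to 300 (SAP 2.1.2). One misplaced AE changes the Treatment Period rate by 1/300 = 0.0033 to 1/250 = 0.0040 events per subject. Assuming 1 to 10 such AEs, the range is 1/300 = 0.003 to 10/250 = 0.040.

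**The case against.** The strongest reply is that few events can be affected. An AE must begin before session 1, lack a day or month, and have a known month or year wholly earlier. Protocol 6.7 lists AEs from the Treatment Period onward and not under Enrollment, and 7.3.3 does not list AE solicitation among the enrollment evaluations; the tick is in Table 2. The floor also errs toward counting more short-term AEs, which is the cautious direction. Both points stand and limit the importance of this one. They do not justify a rule that counts an event when its day is missing and excludes it when its day is known.

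Three stronger readings are tempting, and the documents do not support them.

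- A reader might infer that the Treatment Period starts too late, because prednisone is required "for five days to include the three days before, the day of, and the day after the treatment session" and 3 of the 15 required days (3 sessions × 5 days) precede session 1. The start on the day of the first bronchoscopy is a consistent design choice: Protocol 6.5 says "The Treatment Period will be defined at the Day of 1st procedure bronchoscopy till 6 weeks after the last procedure bronchoscopy", and Protocol 6.7 and SAP 4.6 agree. AEs on those three days remain in the protocol's listing of all reported AEs. Moving the start in SAP 4.6 alone would contradict the protocol.
- A reader might infer that the AE duration summaries in SAP 4.6 will contain negative values. The date table is limited to AE rates, and its only stated extension is to severe exacerbation dates in SAP 6.4. The impossible length is shown only there.
- A reader might infer that between-session AEs will be shifted to session 3. That needs the last-procedure reading, and SAP 4.6 says last when it means last. The wording is ambiguous, but nothing shows that this reading is intended.

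**Conclusion.** The point holds as a minor fault in a stated rule. Applied as written, SAP 6.3 places AEs known to predate treatment in the Treatment Period, leaves the reference procedure undefined, and through SAP 6.4 allows a severe exacerbation to start after it has resolved. The error runs one way: it inflates Treatment Period counts. Each affected AE adds 0.0033 to 0.0040 events per subject. The total cannot be determined from the documents and is probably small.

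This rests on pre-procedure AEs being recorded, which Table 2 and Protocol 8.0 allow, and on some of them having incomplete dates, which the table in 6.3 itself anticipates. It does not bear on the durability conclusion.

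**What to change.** Amend SAP 6.3 in four places:

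1. Replace the reference to the procedure date with the date of the first BT procedure.
2. Apply the floor only when the known month, or the known year if only the year is recorded, contains that date.
3. If the known month or year is wholly earlier, keep the event as pre-treatment, outside the Treatment Period counts.
4. Never impute an onset later than a recorded resolution date.

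SAP 6.4 step 3 takes these up through its existing cross-reference. The definition of the Treatment Period in SAP 4.6 and the protocol stays as it is.

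The cost is a few sentences and a small programming change. SAP 4.7 already provides for an amended plan approved before the analyses are performed. The downside is that Treatment Period counts may fall by a few events; those events would still appear in the protocol's listing of all reported AEs.
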